Power Analysis: This study was initially conceived and powered as a superiority trial. Based on a desire to augment the existing treatment options rather than justify a preferred pharmacotherapy, the design was revised with approval from the study sponsor (see attached approval letter from sponsor). For reference, the original power analysis is below:

Sample size calculations are based on the Aim 1 primary outcome of HIV viral suppression (HIV-1 RNA < 200 copies/mL). We estimate that 340 participants will be required (170 BUP/NX, 170 MMT) to detect a 15% difference in HIV viral suppression between the two study conditions at 12 months, assuming 80% power, alpha of .05, and a viral suppression of 50% in the referral for MMT group. We increase the sample size to 450 participants (225 BUP/NX, 225 MMT) to conservatively account for potential loss to follow-up of 20%. This sample size calculation is additionally conservative in that it does not account for multiple-time-point data that will be available from our longitudinal study. We favor a conservative estimate to off-set the complexity of our proposed mixed logistic model in the data analysis.

Noninferiority Margin: For the primary outcome of viral suppression, we pre-specified a non-inferiority margin of $\leq 13\%$ in the risk difference (RD) comparing BUP to MMT. The noninferiority margin was selected based on margins ranging from 10% to 15% for noninferiority trials testing the effect of antiretrovirals on HIV viral suppression. After choosing the 13% margin, we conducted an informal survey of national HIV-addiction treatment experts who confirmed that it was clinically relevant and appropriate

Data Analysis Plan: Univariate statistics will be used to describe participant characteristics and study outcomes using mean/SD for continuous variables and percentages for categorical variables. Independent samples T-tests will be used to test bivariate differences between the main independent variable (clinic-based BUP/NX versus MMT referral assignment) and baseline continuous variable participant characteristics (e.g., age, CD4 nadir, etc.). Chi-square/Fisher-Exact test will be performed to assess differences between the main independent variable and categorical variables.

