The primary analysis for this study will be a mixed logistic regression model comparing BUP/NX versus MMT on viral suppression rates over time. Treatment comparisons will be performed under the Intent-to-Treat (ITT) criterion; participants will be analyzed in the arm to which they

were randomized regardless of subsequent events. In this mixed logistic model, each (binary) outcome serves as a dependent variable; treatment effect (BUP/NX versus MMT referral) and time effect (e.g., baseline, 6, and 12 months) will be considered main effects. An interaction between these two main effects, e.g., treatment*time, will be included in the model. Model-fitted, marginal risk and RD estimates will be obtained at each time by applying an inverse-logit transformation to coefficients from the logistic regression model, with standard errors estimated via the delta method. We will test the primary hypothesis of noninferiority by comparing the lower bound of a 95% confidence interval to the prespecified margin (i.e., 13%); if the lower confidence limit of the RD is greater than -13%, we will conclude that the BUP/NX is noninferior to MMT. The model will include subject-level random intercepts in order to account for repeated measurements within individuals. Attrition is unavoidable in a longitudinal study; in our study, we anticipate an attrition rate of 20%. The mixed model approach is a recommended strategy for handling missing data in clinical trials under the assumption that the data are missing at random.

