We will conduct three sensitivity analyses. First, we will assume data are missing not at random and use single imputation of unsuppressed for missing VL data. Participants who are lost to follow-up will be imputed as treatment failures (i.e., not suppressed). Death from any cause and dropout will also be considered equivalent to non-suppression for the purposes of this analysis. Second, we will use multiple imputation with Markov-Chain Monte Carlo methods and “auxiliary variables” (i.e., covariates that are not part of the main analysis, but may help predict data missingness) to address missing data. We will include covariates associated with missingness at any time-points (using a relaxed p-value of 0.2) as auxiliary variables in our multiple imputation model. Finally, for our third sensitivity analysis, we will conduct a per-protocol analysis among participants who received at least one dose of study medication in the 90 days before each visit. If sensitivity analysis results change the primary outcome findings, we will report the results alongside our main analysis.

Secondary outcomes including binary ART initiation, ART adherence, and retention in HIV care will be analyzed using similar procedures. As these are superiority hypotheses, we will test them using two-tailed tests at an alpha level of .05.

Aim 2: Assess effect of clinic-based BUP/NX versus MMT referral on opioid use in HIV-infected participants with opioid dependence.

- **H2:** We hypothesize that participants randomized to BUP/NX will have a lower proportion of positive assessments for opioid use (self-report + UDS) at 12 months versus MMT referral

Overview. In Aim 2, we assess the effect of clinic-based BUP/NX on opioid use as measured by urine drug screens or any self-reported use in the last 30 days, assessed at 3, 6, 9, and 12 months following randomization.

Dependent variables. The primary dependent variable for Aim 2 will be the proportion of positive assessments for opioid use at 12 months, as measured by any self-reported opioid use or positive urine drug screen during the 12-month follow-up assessment (binary). We will consider secondary substance use outcomes including proportion of follow-up visits with a positive assessment for opioid use (proportion), and other illicit drug use (binary), and alcohol use (binary).

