Power Analysis: Since our primary outcome in this aim is opioid use, the power analysis is based on this outcome. With our proposed sample size (450 as the total, 225 for each treatment arm), we have gained the power of 91% to detect 15% in difference between the two groups at

the level of alpha 0.05, provided that the proportion of UDS positive for opioid at 12 months will be 65% for MMT referral. This power analysis is conservative due to not maximizing multiple-time-point data from our longitudinal study. We anticipate the power is much higher to off-set the complexity of the mixed logistic model (adjusting for some covariates) we propose in the data analysis plan (see below).

Data Analysis Plan: The primary (binary) outcome for Aim 2 is opioid use, collected at baseline, 3, 6, 9, and 12 months. We will use an approach as in Aim 1.

Aim 3: Assess BUP/NX implementation experience to inform national scale-up of clinic-based BUP/NX.

Overview. We will conduct qualitative interviews with HIV providers, administrators, and opioid dependent participants, and their family members in participating HIV clinics annually during years 1 through 4 to document and describe formative implementation strategies, challenges, and best practices. Results inform policy-making for national scale-up of clinic-based BUP/NX in Vietnam.

Qualitative Procedures and Analysis. The implementation aim documents the experience of providers and participants at clinics to further inform adoption of BUP/NX in Vietnam and guides planning efforts and policy-making. Data also monitor the performance of the sites and qualitative interviews provide critical detail for enhanced understanding of the findings from the trial (Aim 1 and 2). Using the Taxonomy of Mixed Method Designs¹³⁴⁻¹³⁶, our design has a QUAN +Qual structure with simultaneous data collection and emphasis/weight placed on the quantitative efforts. The qualitative data provide complementary information to illuminate and expand the findings from Aims 1 and 2.

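### Aim 2's stated 91% power treats all 225 per arm as evaluable at 12 months; after the plan's own 20% attrition it is about 82–83%

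*Combined protocol and SAP*

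**What the plan says.** The Aim 2 power paragraph (Data Analysis, Aim 2, Power Analysis) states: "With our proposed sample size (450 as the total, 225 for each treatment arm), we have gained the power of 91% to detect 15" percentage points at alpha 0.05, "provided that the proportion of UDS positive for opioid at 12 months will be 65% for MMT referral". It calls this conservative because the repeated visits are not used, and it expects power to be much higher under the covariate-adjusted mixed logistic model. It does not mention attrition. The Aim 2 analysis plan then adopts the Aim 1 approach.

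The direction of the effect comes from H2: participants on BUP/NX "will have a lower proportion of positive assessments for opioid use (self-report + UDS) at 12 months versus MMT referral".

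The origin of 225 per arm is in the Aim 1 Power Analysis, which the plan keeps for reference from the earlier superiority design: "We estimate that 340 participants will be required (170 BUP/NX, 170 MMT) to detect a 15% difference in HIV viral suppression", "assuming 80% power, alpha of .05, and a viral suppression of 50% in the referral for MMT group". It continues: "We increase the sample size to 450 participants (225 BUP/NX, 225 MMT) to conservatively account for potential loss to follow-up of 20" percent. The Aim 1 Data Analysis Plan repeats the rate for the trial: "in our study, we anticipate an attrition rate of 20" percent. For the Aim 1 secondary superiority hypotheses it says "we will test them using two-tailed tests at an alpha level of .05".

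**The concern.** Aim 2 counts as evaluable the same participants whom Aim 1 expects to lose by the same 12-month visit. The two calculations in fact use one pair of proportions. Aim 1 starts at 50% and adds 15 points; Aim 2 starts at 65% and, under H2, subtracts 15. Aim 1 gets 80% power from 170 evaluable per arm. Aim 2 gets 91%, mainly because it uses the enrolled number with no allowance for loss.

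Aim 2 is a superiority hypothesis with its own primary outcome. A reader who meets a null result would take the stated risk of missing a 15-point difference to be 9% and, given the surrounding wording, would suppose it to be lower still. The figure and the wording mislead in the same direction.

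**Working it through.** **Inputs**

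- Enrolled: 225 per arm (Aim 2 Power Analysis).
- Proportions: 65% under MMT referral (Aim 2 Power Analysis). A 15-point reduction under H2 gives 50% under BUP/NX.
- Alpha: 0.05, taken as two-sided. The Aim 2 paragraph does not give sidedness. The plan sets two-tailed tests for the Aim 1 secondary superiority hypotheses, and Aim 2 follows the Aim 1 approach.
- Attrition: 20% (Aim 1 Power Analysis and Data Analysis Plan). Equal loss in both arms is my assumption.
- Evaluable: 225 × 0.80 = 180 per arm.

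**Formula** (normal approximation, pooled variance under the null)

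Power = Φ[(d − 1.96 × SE0) / SE1], with d = 0.15, mean proportion 0.575, SE0 = √(2 × 0.575 × 0.425 / n) and SE1 = √((0.65 × 0.35 + 0.50 × 0.50) / n). The unpooled version is Φ(d / SE1 − 1.96).

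**Step 1: the plan's 91%.** At n = 225, SE0 = 0.04661 and SE1 = 0.04607. Pooled: (0.15 − 1.96 × 0.04661) / 0.04607 = 1.27, power 89.9%. So 91% is, to within about a point, the no-attrition figure. I do not count that one-point gap as a defect.

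**Step 2: after 20% attrition.** At n = 180, SE0 = 0.05211 and SE1 = 0.05151. Pooled: (0.15 − 1.96 × 0.05211) / 0.05151 = 0.93, power 82.4%.

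**Step 3: cross-check on Aim 1.** The same proportions at 170 per arm should return the plan's 80%, and they do. One-sided 0.05 would give about 88% there, so the plan's convention is two-sided.

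| Per arm | Pooled | Unpooled | Exact enumeration of pooled z test |
|---|---|---|---|
| 225 (no attrition) | 89.9% | 90.3% | 89.9% |
| 180 (20% attrition) | 82.4% | 83.0% | 82.1% |
| 170 (Aim 1 evaluable) | 80.2% | 80.8% | 80.9% |

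The arcsine method gives 89.8% at 225 and 82.4% at 180. A continuity-corrected calculation gives 88.0% and 79.4%. Aim 2 comes out slightly above 80% because 170 / 0.80 = 212.5, and the plan enrols 225.

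**Step 4: other readings.** At 180 per arm, one-sided 0.05 gives 89–90%, and 65% versus 80% also gives 89–90%. Both come near 91%, but neither fits the text. The paragraph names 225 per arm, superiority hypotheses are tested two-tailed, and H2 predicts a lower rate.

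**Step 5: covariate adjustment.** The documents give no covariate R², so this is an assumed range, with the variance multiplied by (1 − R²).

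| Assumed R² | 180 per arm | 225 per arm |
|---|---|---|
| 0 | 82–83% | 90% |
| 0.05 | 84–85% | 91–92% |
| 0.10 | 86–87% | 93% |
| 0.20 | 90% | 95% |

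Reaching 91% with 180 per arm would need an R² of about 0.22–0.23.

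**The case against.** The best reply is that the plan does not analyse completers only. It specifies a mixed model under missing at random, with Aim 2 visits at 3, 6, 9 and 12 months, so people lost late still contribute. This is right as far as it goes. As an illustration, assume exchangeable within-person correlation, dropouts observed through month 9, and treatment-by-visit terms. Correlations of 0.3, 0.5 and 0.7 then give an effective 186, 195 and 205 per arm, and power of about 84%, 85% and 87%. So 82–83% is a completers figure, and the planned model may do somewhat better. But even these favourable assumptions do not reach 91%. With visit treated as categorical, full recovery of the missing month-12 values would only return the trial to 225 per arm and about 90%. Any gain beyond that must come from covariates, which the plan does not quantify. Aim 1 also cites unused repeated visits as a source of conservatism, and it still inflates for attrition.

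Two smaller points stand. The 65% is a urine-screen rate, whereas the endpoint is self-report or urine screen, so the control rate could be higher. With the same 15-point difference, 70% or 75% gives about 84% or 86% at 180 per arm (pooled), again short of 91%. And with a continuity correction, power falls just under 80%.

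It is also fair to say that a null result should be read mainly from its confidence interval, and that Aim 2 did not size the trial. That limits the importance of the point but does not make the stated figure correct.

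**Conclusion.** The concern holds. Under the plan's own 20% attrition, Aim 2 has about 82–83% power for 65% versus 50% at two-sided alpha 0.05, about 8 points below the stated 91%. The corresponding chance of missing a true 15-point difference among 12-month completers is about 17–18%, against the 9% implied.

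This rests on equal attrition by arm, two-sided testing, a reduction from 65% to 50%, and a comparison of 12-month proportions without continuity correction. The mixed model and covariates may recover some precision. The documents give neither a within-person correlation nor an R², so the claims that the figure is conservative and that power is much higher have no stated support.

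Power remains above 80% without continuity correction. Aim 2 is not undersized, and no design decision depends on this. The error is in what is reported.

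**What to change.** In the Aim 2 Power Analysis, replace the 91% statement with something like:

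> For 65% versus 50% at two-sided alpha 0.05, power is about 82–83% with 180 evaluable participants per arm after 20% attrition (about 90% with no attrition).

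Then either remove the statements that the figure is conservative and that power is much higher, or support them with a calculation that states its assumed within-person correlation and covariate R². A sentence saying that the mixed model and covariate adjustment may recover some precision can stay. While editing, the authors could also say whether 65% is meant for the urine screen alone or for the composite endpoint.

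The cost is text in one paragraph and a less favourable stated figure. Enrolment, endpoints and analysis do not change.

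### Aim 2 power: repeated visits do not lift power above the stated 91%, because the planned treatment-by-time model draws the 12-month contrast almost wholly from 12-month data

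*Combined protocol and SAP*

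**What the plan says.** All references are to the Data Analysis section of the combined protocol and SAP.

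- **Aim 2, Power Analysis.** The calculation takes all 450 randomised, 225 in each arm, an alpha of 0.05, and a 65% positive rate under MMT referral at 12 months. The power claim reads: "we have gained the power of 91% to detect 15% in difference between the two groups at". A later remark in the same paragraph is: "This power analysis is conservative due to not maximizing multiple-time-point data from our longitudinal study. We anticipate the power is much higher". The plan relies on this margin to absorb the complexity of its mixed model.
- **Aim 2, hypothesis and dependent variables.** H2 and the primary Aim 2 variable are both set at 12 months (binary).
- **Aim 2, Data Analysis Plan.** Opioid use is collected at baseline, 3, 6, 9 and 12 months and analysed by the Aim 1 approach.
- **Aim 1, Data Analysis Plan.** The model has treatment, time and a subject random intercept. "An interaction between these two main effects, e.g., treatment*time, will be included in the model". Risks and risk differences are obtained at each time, and 20% attrition is expected.
- **Aim 1, Power Analysis.** The original superiority calculation, kept for reference, carries a milder remark: "This sample size calculation is additionally conservative in that it does not account for multiple-time-point data".

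**The concern.** A repeated-measures model gains power over a single-visit comparison when it pools the treatment effect across visits. The planned model does the opposite: the interaction lets the effect differ at every visit, and the hypothesis is read off at the last one. In that structure the earlier visits inform the 12-month difference mainly by standing in for participants whose 12-month value is missing.

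The Aim 2 text nevertheless presents repeated visits as a reserve on top of 91%, and uses it to reassure the reader that model complexity is covered. If the reserve is absent, the Aim 2 test has less protection than the plan claims. This is separate from the fact that the 91% deducts nothing for attrition, although the two compound.

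**Working it through.** **Inputs from the plan.** 225 per arm; 65% positive under MMT referral; a 15-point difference with BUP/NX lower, so 50%; alpha 0.05; 20% attrition. Sidedness is not given for Aim 2. I take two-sided from the Aim 1 rule for superiority outcomes ("As these are superiority hypotheses, we will test them using two-tailed tests at an alpha level of .05"), since Aim 2 follows the Aim 1 approach.

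**Assumptions not in the plan.** Time is categorical. Within-person correlation ρ is equal between all visits and ranges from 0.2 to 0.8.

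**1. Reproduce the 91%.** Power = Φ{[0.15√n − 1.96√(2 × 0.575 × 0.425)] / √(0.65 × 0.35 + 0.50 × 0.50)}.

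- n = 225: (2.250 − 1.370) / 0.691 = 1.273, giving **89.9%**.
- An unpooled variance gives 90.3% and the arcsine method 89.8%.

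The stated figure is therefore a single-visit calculation on everyone randomised, and it reproduces to within about a point.

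**2. Complete data under the planned model.** A random-intercept logistic model with separate arm-by-visit levels at 3, 6, 9 and 12 months was simulated. The 12-month marginal risk difference was compared with a 12-month-only analysis of the same data.

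| Random-intercept SD | Simulations | Model power | 12-month-only power |
|---|---|---|---|
| 1 | 300 | 91.3% | 91.3% |
| 2 | 1000 | 90.2% | 89.9% |
| 3 | 300 | 89.3% | 88.3% |

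At SD 2 the empirical standard errors were 0.0463 and 0.0462, and the two estimates correlated at 0.999. Earlier visits add 0 to 1 point.

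**3. With 20% loss.** Using 12-month data alone, n = 225 × 0.8 = 180 and power is (2.012 − 1.370) / 0.691 = 0.929, giving **82.4%**. The most favourable case for the model is that every dropout has all three earlier follow-up visits. Those visits then explain R² = 3ρ² / (1 + 2ρ) of the 12-month outcome, and the effective size is 225 / [(1 − R²)/0.8 + R²].

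| ρ | R² | Effective n per arm | Power | Gain over 82.4% |
|---|---|---|---|---|
| 0.2 | 0.086 | 183.1 | 83.0% | 0.6 |
| 0.5 | 0.375 | 194.6 | 85.2% | 2.8 |
| 0.8 | 0.738 | 211.2 | 87.9% | 5.6 |

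(Gains are from unrounded powers.) As R² approaches 1 the effective size approaches 225, so the ceiling is the 89.9% of step 1. Simulation at SD 2 agrees: 85.2% to 86.4% from the model, against 84.3% from 12-month data alone. The baseline visit was left out because a positive opioid screen is an entry criterion, so it carries almost no information on opioid use.

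**4. What would give a large gain.** These are different analyses from the planned one.

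- One treatment effect common to all four follow-up visits, no interaction: effective n = 225 × 4 / (1 + 3ρ). Power is 93.9% (ρ = 0.8) to 99.9% (ρ = 0.2) with complete data.
- Straight-line time over the four visits: variance factor ρ + 0.7(1 − ρ). Power is 91.6% to 96.0% with complete data, and 84.6% to 91.3% at 180 per arm.

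**5. The same argument applied to the primary test.** Take 50% suppression in both arms, the 13-point margin and a 95% interval. Power = Φ{0.13 / √(0.5/n) − 1.96}: 78.7% at n = 225 and 69.4% at n = 180. With two earlier measurements (baseline and 6 months), R² = 2ρ² / (1 + ρ), and power at 20% loss becomes 70.0% (ρ = 0.2) to 75.9% (ρ = 0.8). The gain is 0.6 to 6.5 points, again below the complete-data figure.

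**The case against.** Four objections deserve weight.

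- **Time is never called categorical.** This is correct, and visit-specific estimates can also come from a linear-time model. Under linear time the complete-data power is modestly above 91%. But the plan lists the time effect as named visits and reports at each of them, so categorical is the natural reading. Even linear time gives only about 85% to 91% at 180 per arm, and it requires a linearity assumption the plan does not make.
- **The Aim 1 remark is different.** A reader might infer that both power sections make the same false claim and that both sentences should go. The documents do not support that. The Aim 1 sentence belongs to the original superiority calculation, labelled as kept for reference, and makes a weaker claim. Under the 20% loss assumed there, earlier visits do recover a little, so the claim is modestly true. That calculation also has a genuine cushion: 450 × 0.8 = 360 evaluable against 340 required (82.4% against 80.2% power).
- **Some gain exists.** A reader might infer that repeated visits are worthless here. They are not: under expected attrition they recover part of the loss.
- **Nothing is miscalculated.** This stands. The 91% and the 170 per arm both reproduce; the fault lies in the qualitative statement attached to the 91%.

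Covariate adjustment, also mentioned under Aim 2, might change precision, but it is not the reason the plan gives for the reserve.

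**Conclusion.** The concern holds for the Aim 2 Power Analysis. Under the planned model, repeated visits do not raise power above the single-visit figure. They add about 0 to 1 point with complete data. At 20% attrition they return about 0.6 to 5.6 of the roughly 7.5 points lost (89.9% to 82.4%), leaving power at about 83% to 88%.

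This rests on categorical time, a two-sided 0.05 test and an assumed correlation range. The size of the recovery depends on the correlation, which the documents do not give, so no fixed upper limit should be written into the plan. Under categorical time, that power stays at or below the complete-data single-visit figure does not depend materially on the correlation.

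For Aim 1 the conclusion is narrower: the historical remark is not an error in its own setting, but it does not carry over as a reserve for the noninferiority test. The validity of the analyses is unaffected.

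**What to change.** 1. **Aim 2, Power Analysis.** Delete the statement that the calculation is conservative and that greater power is anticipated. Replace it with text such as: *Power is that of the 12-month comparison. Under the visit-by-treatment model, earlier visits only partly offset loss to follow-up; at 20% loss the recovery is about 0.6 to 5.6 percentage points for assumed within-person correlations of 0.2 to 0.8.*
2. **Or**, if a gain from repeated visits is wanted, specify an estimand or model that pools visits and compute power for that analysis.
3. **Aim 1, Data Analysis Plan.** State whether time is categorical.
4. **Aim 1, Power Analysis.** Leave the superiority calculation as a record. Add a note that its repeated-visit argument amounts to a modest partial recovery of attrition and is not a reserve for the noninferiority test.

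Items 1, 3 and 4 cost a few sentences, with no change to data collection or sample size; the stated power position becomes less favourable. Item 2 changes what Aim 2 tests and needs a new power calculation.
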